[Part 4 of 9 of the document. The other parts are not shown.]

Subjects who develop seizures will be discontinued from study drug. (revised per Amendment 03) In the event that a subject develops a severe infection, study drug administration should be interrupted for a maximum period of 4 weeks. Examples of severe infections include the following: sepsis; deep tissue (invasive) infection; any infection requiring IV antibiotics; any infection requiring hospitalization (if outpatient at onset); any infection leading to need for oxygen, pressors or fluids to support blood pressure, or intubation; any infection that requires major surgical intervention; pseudomembranous colitis due to *C. difficile*; typhlitis; osteomyelitis; and meningitis. Subjects who recover from severe infections within 4 weeks may resume treatment if deemed appropriate by the investigator after consultation with Medical Monitor. Subjects should permanently discontinue study drug if the severe infection has not resolved within 4 weeks. (revised per Amendment 03)

As described under Dermatologic Assessment in [Section 9.5.1.5.5](#), in the event that a subject develops any skin rash of moderate to severe intensity, or any rash lasting more than 72 hours regardless of severity (with the exception of oral or genital herpes as described in the next paragraph), study drug administration should be interrupted for a maximum period of 4 weeks and a dermatologic consult will be requested regardless of whether the rash is considered drug related or due to other causes. For cases where the investigator suspects a drug rash, regardless of severity, the subject will be discontinued from study drug, a dermatologic consult will be requested, and a skin biopsy will be performed to confirm the diagnosis. The skin rash will be treated as per standard care and will be followed up until resolution regardless of etiology or severity. Subjects who recover from skin rash within 4 weeks may resume treatment if in the opinion of the dermatologic consult, the rash was not drug related and it is deemed appropriate by the investigator after consultation with Medical Monitor. Subjects should permanently discontinue study drug if the skin rash has not resolved within 4 weeks or returns during rechallenge. (revised per Amendment 03)

In the event that a subject develops moderate to severe oral or genital herpes, study drug administration should be interrupted for a maximum period of 4 weeks. Subjects who develop a mild case of oral or genital herpes may remain on study drug even if the event lasts more than 72 hours. Subjects who recover from moderate to severe oral or genital herpes within 4 weeks may resume treatment if it is deemed appropriate by the investigator after consultation with Medical Monitor. Subjects should permanently discontinue study drug if the oral or genital herpes has not resolved within 4 weeks or returns during rechallenge. (revised per Amendment 03) Subjects who discontinue study drug early must complete the ED Visit (within 7 days of the last dose of study drug) and the Follow-Up Visits (1 and 3 months after the last dose of study drug). These Follow-Up Visits will be conducted to monitor efficacy and safety parameters after early withdrawal from the study or discontinuation of study drug.

All subjects who discontinue study drug before reaching 12 months of treatment will also be asked to return to the clinic for a 12-month clinical assessment and then again at 24 months. Subjects who discontinue treatment between 12 and 24 months of treatment will be asked to

return to the clinic for a 24 month clinical assessment. Subjects who discontinue early from study drug are considered “on study” as long as they continue to return for their regularly scheduled clinical assessments at 12 and 24 months as outlined above, at which efficacy and quality of life will be assessed along with concomitant medications and AEs. However, subjects who discontinue study drug early are not considered to have ‘completed’ the study as a final Subject Disposition.

The primary reason for discontinuation and all other reason(s) contributing to the subject’s discontinuation from study drug(s) should be collected on the ED from study drug electronic case report form (eCRF) page. In addition, the date of last dose of study drug(s) will be recorded on the Study Drug Dosing eCRF page. If a subject discontinues study treatment and the study at the same time, the end-of-study procedures (Final Visit) will be followed (see [Section 9.5.5](#)).

9.4 Treatment(s)

9.4.1 Treatment(s) Administered

For this study the test drug is elenbecestat (E2609) and the control drug is placebo. All study drug is to be administered orally, once daily (QD), in the morning with or without food. As shown in [Figure 1](#), there will be 2 treatment arms where the elenbecestat (E2609) arm will be administered a single dose of 50 mg per day and the control arm will be administered placebo.

Study treatment will begin on Day 1 (at the study site) following randomization and will continue for approximately 24 months. Please refer to [Table 3](#) and [Section 9.5.1.4.1](#) for specific information regarding study drug administration on days when PK sampling is to be performed.

Study drug dose will remain the same for each individual subject throughout the duration of the study. If a subject develops a concurrent illness during the treatment period, the investigator should discuss with the medical monitor on whether dosing with study drug needs to be temporarily suspended. As a general clinical guideline, dosing with study drug may be resumed after resolution or stabilization of the concurrent illness, after discussion with the medical monitor.

Rules for discontinuing study treatment for subjects due to skin rash or to severe infections are described in [Section 9.5.1.5.5](#).

9.4.2 Identity of Investigational Product(s)

Elenbecestat (E2609) will be supplied by the sponsor as tablets of 50-mg dose strength in bottles of 35 tablets each. Placebo tablets to match elenbecestat (E2609) will be of identical appearance. Each subject will receive 1 tablet of 50 mg elenbecestat (E2609) or an identical placebo tablet, to be administered orally QD in the morning with or without food. The product release certificates for elenbecestat (E2609) and placebo will be included in the clinical study report for this protocol.

Subjects will be stratified and randomized, and drug will be dispensed, via an interactive voice and web response system (IxRS) system (see [Section 9.4.3](#)).

The sponsor will provide the study drugs packaged in a double-blind configuration. Each subject's study tablets will consist of either elenbecestat (E2609) or placebo (see [Section 9.4.2.3](#) for labeling details).

9.4.2.1 Chemical Name, Structural Formula of Elenbecestat (E2609)

- Test drug code: E2609
- Generic name: elenbecestat (pINN)
- Chemical name: International Union of Pure and Applied Chemistry
N-{3-[(4*aS*,5*R*,7*aS*)-2-Amino-5-methyl-4*a*,5-dihydro-4*H*-furo[3,4-*d*][1,3]thiazin-7*a*(7*H*)-yl]-4-fluorophenyl}-5-(difluoromethyl)pyrazine-2-carboxamide
- Molecular formula: C₁₉H₁₈F₃N₅O₂S
- Relative molecular mass: 437.44

9.4.2.2 Comparator Drug

Not applicable.

9.4.2.3 Labeling for Study Drug

Elenbecestat (E2609) will be labeled in accordance with text that is in full regulatory compliance with each participating country and is translated into the required language(s) for each of those countries. The following information may be included but is not limited to:

- Protocol number
- For clinical study use only
- Name and address of the sponsor
- Chemical name/drug identifier
- Lot number/batch number
- Storage conditions, expiration date if necessary

9.4.2.4 Storage Conditions

Study drug will be stored in accordance with the labeled storage conditions. Temperature monitoring is required at the storage location to ensure that the study drug is maintained within an established temperature range. The investigator or designee (or if regionally required, the head of the medical institution) is responsible for ensuring that the temperature is monitored throughout the total duration of the study and that records are maintained; the temperature should be monitored continuously by using either an in-house validated data acquisition system, a mechanical recording device, such as a calibrated chart recorder, or by

manual means, such that minimum and maximum thermometric values over a specific time period can be recorded and retrieved as required.

9.4.3 Method of Assigning Subjects to Treatment Groups

Subjects will be assigned to treatments based on a computer-generated randomization scheme that will be reviewed and approved by an independent statistician. The randomization scheme and identification for each subject will be included in the final clinical study report for this study. The doses and number of treatment groups to be used are described in [Section 9.4.1](#).

Stratification and randomization will be performed centrally by an IxRS. The IxRS or clinical supply vendor will generate the randomized bottle identification numbers. At enrollment (Screening), the investigator or designee will call the IxRS to register the subject information. At randomization (Visit 2), the IxRS will assign each subject a unique randomization number.

9.4.4 Selection of Doses in the Study

Selection of elenbecestat (E2609) 50 mg per day is based on the results (PD, safety, and tolerability) from the completed Phase 1 studies and interim data from the ongoing Phase 2 Study 202. Study 202 is currently evaluating the PD effects (reduction from baseline in CSF A β levels) of 5, 15, and 50 mg of elenbecestat (E2609) given daily. An interim PD analysis has been performed on the degree of CSF A β reduction achieved with elenbecestat (E2609) 5, 15, and 50 mg per day. Based on the PK/PD modeling results, elenbecestat (E2609) 50 mg per day reduced median CSF A β by approximately 70%. (revised per Amendment 03) Based on these data, elenbecestat (E2609) 50 mg per day dose was selected as a viable dose for this study. Subjects will be stratified according to region (7 levels), clinical dementia staging with no more than approximately 25% of the randomized subjects diagnosed with the early stages of mild dementia due to AD, and concurrent AD medication use. (revised per Amendments 01 and 02)

9.4.5 Selection and Timing of Dose for Each Subject

Elenbecestat (E2609) is administered orally, QD, in the morning with or without food. Study treatment will begin on Day 1 following randomization and will continue for 24 months.

9.4.6 Blinding

Elenbecestat (E2609) and placebo will be administered as tablets of identical appearance.

During the Randomization and Follow-Up Phases, subjects and all personnel involved with the conduct and interpretation of the study, including investigators, site personnel, and sponsor staff will be blinded to the treatment codes (double-blind). Randomization data will be kept strictly confidential, filed securely by an appropriate group with the sponsor or CRO, and accessible only to authorized persons (eg, Eisai Global Safety) until the time of unblinding, per the standard operating procedure.

PK and PD data will be provided to the sponsor by the PK and PD analysis laboratories using dummy subject numbers instead of actual subject numbers. The same dummy subject number will be used for a subject's PK and PD data. These data will be used to evaluate whether the PK and PD effects seen in this study are similar to those seen in previous studies. Thereafter, unblinded PK and PD data will only be provided to the sponsor after study completion.

In the event that emergency conditions require knowledge of the study treatment given, the blind may be broken via the code breaker facility within the IxRS. Emergency procedures for revealing drug codes are given in [Section 9.5.4.5](#). If possible, before breaking the blind, the investigator should consult with the sponsor to ascertain the necessity of breaking the code. If an AE results in the investigator breaking the blind, then that AE must be reported as a SAE.

9.4.7 Prior and Concomitant Therapy

Any medication (including over-the-counter medications) or therapy administered to the subject prior to the study (within 6 months of randomization) and during the study (starting at the date of informed consent) will be recorded on the Prior & Concomitant Medication eCRF or Non-Pharmacological Procedures eCRF. The investigator will record on the Adverse Event eCRF any AE for which the concomitant medication/therapy was administered. If the concomitant medication/therapy is being administered for a medical condition present at the time of entry into the study, the investigator will record the medical condition on the Medical History and Current Medical Condition eCRF.

Listings of prohibited and permitted drugs are provided in [Appendix 2](#) (Prohibited medications are presented in [Listing 1](#), [Listing 2](#), and [Listing 3](#). Medications that are permitted with restrictions are listed in [Listing 4](#), [Listing 5](#), and [Listing 6](#)).

The following agents are not permitted before randomization (specific time frames are shown below) and until the last visit during the treatment period: (revised per Amendment 02)

- a) Immunoglobulin therapy and biologic drugs are not permitted within 6 months before Screening and until the last visit during the treatment period (revised per Amendment 02)
- b) Systemic or ocular immunosuppressive or immunomodulatory drugs are not permitted for a period of 5 half-lives or 60 days (whichever is longer) before randomization and until the last visit during the treatment period (revised per Amendment 02)
- c) Moderate to strong inhibitors of carboxylesterase 2 (CES2) enzyme activity are not permitted for a period of 5 half-lives or 7 days (whichever is longer) before randomization and until the last treatment visit. Simvastatin use is permitted only with QD evening administration.
- d) Live/live attenuated vaccines are not permitted within 3 months before randomization and until the last treatment visit (this does not apply to non-live/inactivated vaccines) (revised per Amendment 02)

Concomitant therapy with AChEI or memantine should only be allowed and/or acceptable for the region or country in which the study is being conducted and should follow the local standard of care for symptomatic treatment (revised per Amendment 02). Subjects who are taking AChEI or memantine will be required to be on a stable dose for at least 12 weeks before randomization. Initiation of therapy or changing dose of AChEIs or memantine during the study should be undertaken in compliance with local standard of care for symptomatic treatment of AD. (revised per Amendment 03) Subjects who start on AChEI or memantine or change their dose during the Treatment Period will be permitted to continue in the study; however, subjects should not undertake cognitive assessments until they have been on a stable dose for at least 4 weeks.

Subjects who are taking other medications will be required to be on a stable dose for at least 4 weeks before randomization, except for medications which are administered as short courses (eg, up to 3 weeks unless discussed and agreed with Medical Monitor) of treatment (eg, anti-infectives, oral steroids) or which are to be used on a PRN basis. (revised per Amendment 01) Concomitant medications (including benzodiazepines and opiates) which are used on a PRN basis and which are central nervous system (CNS) active and may affect cognitive function are not permitted during a period of 72 hours prior to cognitive testing.

For subjects who undergo an LP for collection of CSF: Subjects who are on anticoagulants may have a variable dose but should have stable anticoagulation control for at least 4 weeks before the LP procedure. Subjects may be required to stop their anticoagulant medication prior to CSF collection and then restart this medication after the LP procedure, as per local guidelines.

Either aspirin or clopidogrel (or any other antiplatelet drug which is not aspirin) is permitted in all subjects. Aspirin and clopidogrel (or any other antiplatelet drug which is not aspirin) in combination are also permitted but subjects who are on such a combination of antiplatelet drugs may be required to stop 1 or more of these antiplatelet drugs before the LP procedure and restart after the LP as per local guidelines.

Subjects who initiate treatment with drugs not intended for treatment of cognitive impairment during the study should continue in the study if in the opinion of the investigator this will not interfere with study procedures or subject safety and are not prohibited above. However, if such drugs may affect cognitive function, subjects should not undertake cognitive assessments until they have been on a stable dose for at least 4 weeks.

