9.7.1.8.3 LABORATORY VALUES

Laboratory results will be summarized using International System of Units, as appropriate. For all quantitative parameters listed in [Section 9.5.1.5.3](#), the actual value and the change from baseline to each postbaseline visit and to the end of treatment (defined as the last on-treatment value) will be summarized by visit and treatment group using descriptive statistics. Qualitative parameters listed in [Section 9.5.1.5.3](#) will be summarized using frequencies (number and percentage of subjects), and changes from baseline to each postbaseline visit and to end of treatment will be reported using shift tables. Percentages will be based on the number of subjects with both nonmissing baseline and relevant postbaseline results.

Laboratory test results will be assigned a low/normal/high (LNH) classification according to whether the value was below (L), within (N), or above (H) the laboratory parameter's reference range. Within-treatment comparisons for each laboratory parameter will be based on 3-by-3 tables (shift tables) that compare the baseline LNH classification to the LNH classification at each postbaseline visit and at the end of treatment. Similar shift tables will also compare the baseline LNH classification to the LNH classification for the highest and lowest value during the treatment period.

[Appendix 1](#) (Sponsor's Grading for Laboratory Values) presents the criteria that will be used to identify subjects with treatment-emergent markedly abnormal laboratory values (TEMAVs). Except for phosphate, a TEMAV is defined as a postbaseline value with an increase from baseline to a Grade of 2 or higher. For phosphate, a TEMAV was defined as a postbaseline value with an increase from baseline to a Grade of 3 or higher. When displaying the incidence of TEMAVs, each subject may be counted once in the laboratory parameter high and in the laboratory parameter low categories, as applicable.

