Appendix 2 List of Permitted and Prohibited Prior/Concomitant Medications

Prohibited medications are shown in [Listing 1](#), [Listing 2](#), and [Listing 3](#). Medications permitted with restrictions are listed in [Listing 4](#), [Listing 5](#), and [Listing 6](#). These may not be all-inclusive listings. Please contact the medical monitor(s) if the investigators have any questions or concerns regarding any medication not listed that your subjects may be taking before enrollment or start during the course of the E2609-G000-301 study.

Antibiotics, analgesics, and anti-inflammatory drugs intended for short courses of treatment are permitted and do not need to follow the restrictions of [Listing 6](#) for a stable dose of 4 weeks before Baseline. If these medications may affect cognitive function but the medications are clinically indicated, then cognitive testing should not take place until at least 72 hours after the last dose of the course of treatment.

Prohibited Prior/Concomitant Medications

Listing 1 Prohibited Medications Within 5 Half Lives or 7 Days, Whichever is Longer, Before Randomization and Until the Last Visit During the Treatment Period

Moderate to Strong Inhibitors of Carboxylesterase 2 (CES2) Enzyme Activity
Generic name
Loperamide
Orlistat
Telmisartan
Fenofibrate
Carvedilol
Manidipine
Diltiazem
Verapamil

NOTE: Simvastatin use is permitted only with once daily evening administration.

Listing 2 Prohibited Medications Within 5 Half Lives or 60 Days, Whichever is Longer, Before Baseline and Until the Last Visit During the Treatment Period

Systemic or Ocular Immunosuppressants^a and Immunomodulatory Drugs (revised per Amendment 02)	
Prednisolone	Deltasone, Prednicot, Prednisone Intensol, Rayos, Sterapred, Sterapred DS
Methylprednisolone	Medrol, Meprolone
Dexamethasone	Decadron, Dexasone, Diodex, Hexadrol, Maxidex
Azathioprine	Azasan, Imur
Mycophenolate	CellCept, Myfortic
Fingolimod	Gilenya
Methotrexate	Trexall
Ciclosporine	Gengraf, Neoral

Prohibited Medications Within 6 Months Before Screening and Until the Last Visit During the Treatment Period (revised per Amendment 02)

Immunoglobulin Therapy and Biologic Drugs (revised per Amendment 02)	
Ranibizumab	Lucentis
Bevacizumab	Avastin
Infliximab	Remicade
Etanercept	Enbrel
Adalimumab	Humira
Omalizumab	Xolair
Efalizumab	Raptiva

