NOTE: Subjects may undergo both the amyloid PET and CSF assessments, but need a positive amyloid result in only 1 of the 2 procedures to confirm eligibility. Subjects who consent to amyloid PET or CSF for eligibility purposes are not required to participate in the amyloid PET or CSF longitudinal substudies. Use of a historical amyloid PET (conducted within 12 months before the planned date of randomization) is acceptable for determination of eligibility but will not suffice for the baseline assessment if the subject wishes to consent to the amyloid PET longitudinal substudy. The historical imaging data must be made available to the sponsor.
5. Male or female subjects between 50 and 85 years of age, inclusive at the time of consent
6. If receiving an AChEI or memantine or both for AD, must be on a stable dose for at least 12 weeks prior to Randomization. Treatment-naïve subjects with AD can be entered into the study.
7. Subjects must have been on stable doses of all other (ie, non-AD related) permitted concomitant medications for at least 4 weeks prior to Randomization, except for medications which are administered as short courses (eg, up to 3 weeks unless discussed and agreed with Medical Monitor) of treatment (eg, anti-infectives, oral steroids) or which are to be used on a Pro re nata

(PRN) basis. Subjects who require a short course of treatment, such as anti-infectives or oral steroids, may be randomized once the acute illness has completely resolved, even if the concomitant medication continues. (revised per Amendment 01)

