7. Subjects must have been on stable doses of all other (ie, non-AD related) permitted concomitant medications for at least 4 weeks prior to Randomization, except for medications which are administered as short courses (eg, up to 3 weeks unless discussed and agreed with Medical Monitor) of treatment (eg, anti-infectives, oral steroids) or which are to be used on a Pro re nata (PRN) basis. Subjects who require a short course of treatment, such as anti-infectives or oral steroids, may be randomized once the acute illness has completely resolved, even if the concomitant medication continues. (revised per Amendment 01)
8. Must have an identified study partner (defined as a person able to support the subject for the duration of the study and who spends at least 8 hours per week with the subject). The study partner must provide written informed consent. In addition, this person must be willing and able to provide follow-up information on the subject throughout the course of the study. This person must, in the opinion of the investigator, spend sufficient time with the subject on a regular basis such that they can reliably fulfill the requirements of being a study partner. A study partner need not be living in the same residence with the subject. For such a study partner not residing with the subject, the investigator has to be satisfied that the subject can contact the study partner readily during the times when the study partner is not with the subject. Study partners need to provide input to the following assessments: CDR, FAQ, EQ-5D, QOL-AD, Zarit's Burden Interview, NPI-10, and the clinical assessment of suicidality. (revised per Amendment 01) Consideration can occur for the investigator to decide whether the study partner can provide information over the telephone or whether the study partner must attend the study visits in person with the subject.

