 - Thyroid stimulating hormone (TSH) above normal range. Other tests of thyroid function with results outside the normal range should only be exclusionary if they are considered clinically significant by the investigator (this applies to all subjects whether or not they are taking thyroid supplements)
 - Abnormally low (below LLN) serum Vitamin B12 levels (if subject is taking Vitamin B12 injections, level should be at or above the LLN)
10. Subjects at risk of increased risk of infection, specifically:
 - Subjects with chronic viral hepatitis, a history of active tuberculosis disease (TB), ophthalmic shingles or ocular herpes simplex virus (HSV) infection
 - Any active infection within the last 4 weeks before randomization. For such cases, the timing of randomization can be extended (up to 4 weeks) to allow the infection to resolve
 - Any immunological disease which is not adequately controlled, or which requires treatment with biologic drugs during the study. History of immunoglobulin deficiency or other immunodeficiency disorders (including subjects known to be HIV positive)
11. Have received any live vaccine/live attenuated vaccine in the 3 months before randomization (revised per Amendment 01)
12. Any chronic inflammatory disease that is not adequately controlled or that requires systemic or ocular immunosuppressive or immunomodulatory therapy.

NOTE: The following subjects do not need to be excluded:

- Subjects with seasonal or perennial allergic rhinitis, asthma, or chronic obstructive pulmonary disease where the condition is considered to be stable and adequately controlled by inhaled steroids.
 - Hashimoto's thyroiditis but who are stable on thyroid replacement therapy and not on systemic immunosuppressive therapy.
 - Cutaneous manifestations of immunological disease that do not require systemic immunosuppressive therapy or systemic immunomodulatory therapy (ie, topical steroid treatment is permitted)
13. Any other clinically significant abnormalities, such as:
- Physical examination, vital signs, laboratory tests or ECG at Screening or Baseline which in the opinion of the investigator require further investigation or treatment or which may interfere with study procedures or safety.

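### Section 9.4.7 bars systemic steroids for at least 60 days before randomization, yet lists oral steroids among the short courses accepted within the last 4 weeks

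*Protocol*

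**What the plan says.** Two versions matter here. Sections 9.4.7 and 9.7.1.8.3 and Appendix 2 are available in the current text (Amendment 03). The synopsis and Sections 9.3.1 and 9.3.2 are available only up to Version 3.0 (Amendment 02), so their current wording could not be checked.

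**Current text, the ban.** Section 9.4.7, item b: "Systemic or ocular immunosuppressive or immunomodulatory drugs are not permitted for a period of 5 half-lives or 60 days (whichever is longer) before randomization". The ban then runs to the last treatment-period visit. Appendix 2 repeats the window ("Listing 2 Prohibited Medications Within 5 Half Lives or 60 Days, Whichever is Longer, Before Baseline") and names prednisolone (with prednisone brands), methylprednisolone and dexamethasone. Footnote a exempts only topical and inhaled products.

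**Current text, the permission.** Further on, Section 9.4.7 requires other medications to be at a stable dose for 4 weeks before randomization, except those "administered as short courses (eg, up to 3 weeks unless discussed and agreed with Medical Monitor) of treatment (eg, anti-infectives, oral steroids") or used as needed. The opening of Appendix 2 adds: "Antibiotics, analgesics, and anti-inflammatory drugs intended for short courses of treatment are permitted".

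**Version 3.0.** Inclusion criterion 7 (Section 9.3.1) says that subjects who need a short course, "such as anti-infectives or oral steroids, may be randomized once the acute illness has completely resolved, even if the concomitant medication continues". The synopsis has the same sentence. Exclusion 12 covers "Any chronic inflammatory disease that is not adequately controlled or that requires systemic or ocular immunosuppressive or immunomodulatory therapy", and exclusion 18 bars anyone on a prohibited drug. Sections 9.2.2 and 9.3 say that meeting any exclusion makes a subject ineligible for study drug.

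**The concern.** One section gives two incompatible answers for the same subject. Someone who took oral prednisolone two weeks before randomization is barred by item b and Listing 2, but matches the short-course example. A site acting on the example randomizes a subject whom the ban excludes, and another site acting on item b turns the same subject away.

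The rule serves immune safety. Section 7.1 (Version 3.0) reports lymphocyte reductions with the study drug and proposes lymphocytes as a monitoring marker. Table 3 draws hematology at Visit 2, and Section 9.7.1.8.3 judges laboratory grades against baseline: apart from phosphate, "a TEMAV is defined as a postbaseline value with an increase from baseline to a Grade of 2 or higher". A drug that the protocol itself classes with immunosuppressants, if still being taken at Visit 2, would therefore be present when the baseline lymphocyte count is drawn.

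**Working it through.** The protocol states no figure to reproduce. The check compares two windows that both end at randomization.

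**Inputs**
- Minimum washout W, from item b and Listing 2: the longer of 5 half-lives and 60 days, so W ≥ 60 days whatever the half-life. Item b counts from randomization and Listing 2 from Baseline. Both are Visit 2, so this makes no material difference.
- Stable-dose window S, from the short-course sentence in 9.4.7: 4 weeks, S = 4 × 7 = 28 days.
- d = days from the last systemic steroid dose to randomization.

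**Step 1. When does the short-course exemption do any work?** It lifts a requirement about the last 28 days. A drug stopped before then does not need it. The exemption therefore matters only when 0 ≤ d ≤ 28.

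**Step 2. Does that range overlap what item b allows?** Item b requires d ≥ 60. Since 28 < 60, no value of d satisfies both. For every steroid on Listing 2, using the exemption means breaching the ban.

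**Step 3. Size of the breach.** Shortfall = 60 − d, and more if 5 half-lives exceed 60 days.

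| Situation | d | Shortfall |
|---|---|---|
| Last dose at the far edge of the 28-day window | 28 | 60 − 28 = 32 days |
| 21-day course begun 28 days before randomization | 28 − 21 = 7 | 60 − 7 = 53 days |
| Course still running at randomization (Version 3.0, criterion 7) | 0 | 60 − 0 = 60 days |

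The range is 32 to 60 days. In the last case the course would also breach the part of item b that applies during treatment.

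**Step 4. Does other text reconcile the rules?**
- Footnote a of Listing 2 does not: it covers route of administration, not duration of use.
- The Appendix 2 opening does not: it speaks of anti-inflammatory drugs without saying whether the listed corticosteroids are meant.
- In Version 3.0, exclusion 18 together with Sections 9.2.2 and 9.3 gives a formal answer, which is exclusion. Criterion 7 still tells the site, in terms, that the subject may be randomized.

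**The case against.** The best counter-argument is that the short-course sentence only waives a stability requirement and permits nothing. It comes after the list of banned agents and does not lift it. The paragraph that follows in 9.4.7 limits drugs started during the study to those not banned above, the first sentence of criterion 7 speaks of permitted medications, and the Appendix 2 opening waives only the Listing 6 restriction. On that reading, oral steroids are simply a badly chosen example.

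This does not remove the conflict. The short-course sentence refers to other medications without the limit that the later paragraph carries. Oral steroids are one of only two examples given, and on the waiver-only reading the example would be empty for every listed steroid. The second sentence of criterion 7 is an outright permission to randomize.

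Several points on the other side do stand:
- The strongest permissive wording, and with it the 60-day end of the range, comes from Version 3.0 and may have changed since.
- Read formally, Version 3.0 resolves to exclusion.
- Only a course running at or near Visit 2 bears on the baseline sample. The documents give neither size nor direction for a steroid effect on lymphocytes.
- The dose-interruption rule in Section 9.3.3 (Version 3.0) uses an absolute count below 800/mm³, so it does not depend on baseline.
- The short-course text was revised under Amendment 01, so the sponsor may have meant to allow such courses. Which rule should prevail is the sponsor's decision.

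**Conclusion.** The concern holds on the current text alone. Item b, Listing 2 and its footnote cannot be applied together with the short-course example for systemic corticosteroids. A subject admitted under the example is at least 32 days short of the stated washout, and 60 days short if the Version 3.0 permission to continue the drug still applies.

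The conclusion assumes that oral steroids in 9.4.7 include the agents named in Listing 2. No half-life is needed, because 60 days is the minimum. The documents give no frequency of short-course steroid use, so the number of affected subjects is unknown. No imbalance between arms is claimed, nor any effect on type I error, power or the CDR-SB estimate. What needs correcting is an eligibility and immune-safety rule that sites cannot follow as written.

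**What to change.** Let one rule govern throughout. The default below fits Listing 2, its footnote and exclusions 12 and 18:

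1. Delete oral steroids from the short-course examples in 9.4.7, from both sentences of inclusion criterion 7 if they are still there, and from the matching synopsis text.
2. In the opening of Appendix 2, write *anti-inflammatory drugs (other than the systemic corticosteroids in Listing 2)*.

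If the sponsor does intend to accept short oral courses, put the exemption into item b and the Listing 2 footnote, with a maximum duration and a minimum washout before randomization, both set by the sponsor's physicians. Then repeat the same wording in criterion 7 and Appendix 2.

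The cost is an amendment to wording and a memo to sites, with no added procedures. Under the default, a few subjects who need a steroid course during screening will be delayed, rescreened or excluded.
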